7.3.1.1. ISR Analyses

- Summaries for total ISR's, both as number of events, event rates adjusted to exposure and patient counts and percentages will be provided.

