All safety data will be summarized using either summary statistics or frequency tabulations, as appropriate to the type of data. Adverse events will be coded using Medical Dictionary for Regulatory Activities (MedDRA). Adverse events will be grouped by system organ class (SOC) and preferred term (PT) and summarized as described above. Only treatment emergent AEs will be summarized. Treatment emergent AEs (TEAEs) are defined as all AEs that start or worsen on or after the start of first study drug administration in the present study and before the start of the optional treatment extension (for the 1 year analysis). For patients who do not participate in the optional treatment extension, events that start >28 days after the last dose of study medication will not be defined as TEAEs. In addition to the frequency counts and percentages, the TEAEs will be presented as annualized rates. The annualized rates will be calculated by the total number of reported AEs divided by the total exposure time measured as the total subject years of exposure to the study medication.

Primary safety analyses will be based on TEAEs with a focus on AESI, i.e., infusion site reactions, hypersensitivity and polyneuropathy. Summaries of total number of cases will be presented as number of events, event rates adjusted to exposure and patient counts and percentages. For hypersensitivity and polyneuropathy, summaries will be broken down by outcomes (unknown, recovered, not yet recovered, recovered with sequelae and death); time to onset will be presented by Kaplan Meier figures, and with descriptive statistics. The Visual Analogue Scale (VAS) pain score will be summarized with descriptive statistics by visit and treatment group, changes from baseline will be summarized and the proportion of patients with a VAS pain score >0 mm or \geq 40 mm will be tabulated by visit and treatment group.

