11.1.4.1.2 Analyses of Infusion Site Reactions

• Summaries for total infusion site reactions, both as number of events, event rates adjusted to exposure and patient counts and percentages will be provided.

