11.1.4.1.6 Tolerability

Tolerability will be assessed based on percentage of subjects that complete the 12month treatment period (or long-term extension) of the study and the percentage of subjects who discontinue from the 12-month treatment period (or long-term extension) due to a TEAE. Time (days) from enrolment to discontinuation will be illustrated as Kaplan-Meier curves by treatment regimen. Patients who complete the study will be right censored at the date of last dose of study treatment during the 12-month study period (or long-term extension). Time to discontinuation will also be explored by recruitment wave 1 and 2 following corrective actions for patients' retention.

Local safety expressed by erythema, edema and Draize scores as well as assessment of nodules and hematomas (number and severity) will be listed but not summarized.

The safety data from the treatment extensions up to Month 102 will be combined with the safety data of the main study and will be analyzed similarly as defined above.

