7.3.1.2. Hypersensitivity Analyses

- Summaries for total Number of Hypersensitivity cases (by SOC and PT), will be presented as number of events, event rates adjusted to exposure and patient counts and percentages.
- Time to onset of Hypersensitivity will be presented by Kaplan Meier figures. In these analyses, the patients who did not experience Hypersensitivity will be right censored at the time of the last visit.
- Time from onset of Hypersensitivity to resolution will be presented with descriptive statistics. Unresolved cases will be right censored at the last visit.
- Summaries for total number of Hypersensitivity will be broken down by Outcomes (unknown, recovered, not yet recovered, recovered with sequelae and death) and will be presented as number of events, event rates adjusted to exposure and patient counts and percentages.

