7.3.1.3. Polyneuropathy Analyses

- Summaries for total Number of Polyneuropathy cases (by SOC and PT), will be presented as number of events, event rates adjusted to exposure and patient counts and percentages.
- Time to onset of Polyneuropathy will be presented by Kaplan Meier figures. In these analyses, the patients who did not experience Polyneuropathy will be right censored at the time of the last visit.
- Time from onset of Polyneuropathy to resolution will be presented with descriptive statistics. Unresolved cases will be right censored at the last visit
- Summaries for total number of Polyneuropathy will be broken down by Outcomes (unknown, recovered, not yet recovered, recovered with sequelae and death) and will be presented as number of events, event rates adjusted to exposure and patient counts and percentages.

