7.3.2. VAS Score for Pain

The VAS pain score will be summarized with descriptive statistics by visit and treatment group. In addition, the changes from baseline will be summarized. Furthermore, the proportion of patients with a VAS pain score >0 mm or ≥ 40 mm will be tabulated by visit and treatment group.

7.3.3. Additional Local Safety Measures.

Local safety expressed by erythema edema and draize scores as well as assessment of nodules and hematomas (number and severity) will be listed but not summarized.

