- A table of the overall incidence (number and percentage) of patients reporting TEAEs and the number of TEAE events and event rates adjusted to exposure, drug-related TEAEs, severe TEAEs, serious TEAEs, TEAEs leading to study treatment discontinuation, TEAEs leading to dose adjustment/temporary withdrawal, and TEAEs leading to death
- TEAEs by SOC and PT, both as number of events, event rates adjusted to exposure and patient counts and percentages
- TEAEs by PT, both as number of events, event rate adjusted to exposure, patient counts, sorted by descending frequency of patients reporting TEAEs in Regimens 1
- Drug-related TEAEs by PT, both as event, event rate adjusted to exposure and patient counts and percentages
- Severe TEAEs by PT, both as event, event rate adjusted to exposure and patient counts and percentages

- Drug-related TEAEs by SOC, PT and severity both, as event, event rate adjusted to exposure and patient counts and percentages
- Serious TEAEs by PT, both as event, event rate adjusted to exposure and patient counts and percentages
- TEAEs leading to study treatment discontinuation, both as event, event rate adjusted to exposure and patient counts and percentages
- TEAEs leading to dose adjustment/temporary withdrawal, both as event, event rate adjusted to exposure and patient counts and percentages
- TEAEs classified by SOC, PT and the time of onset both as event, event rate adjusted to exposure and patient counts and percentages. For this summary, the time of onset will be classified as <7 days, 7-30 days or >30 days

In addition, the following analyses will be performed for the most common or relevant TEAEs (at least for the 10 most commonly reported PTs in both regimens 1 and 3 including also dyskinesia in case it is not among the 10 most common ones):

- The time to first onset of each TEAE within each treatment group will be summarized with Kaplan-Meier methods. In these analyses, the patients who did not experience the AE in question will be censored at the time of the last visit. Separate Kaplan-Meier plots (including separate curve for each treatment group) will be done for each PT.

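### No planned table shows whether infusion-site reactions healed, persisted or left sequelae, although outcome is collected for every AE and tabulated for the other two AESIs

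*SAP*

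**What the plan says.** For infusion-site reactions, the whole of SAP 7.3.1.1 is one bullet: "Summaries for total ISR's, both as number of events, event rates adjusted to exposure and patient counts and percentages will be provided". Protocol 11.1.4.1.2 is the matching single bullet, beginning "Summaries for total infusion site reactions, both as number of events".

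The other two AESIs get more. The statistical part of the Protocol synopsis reads "For hypersensitivity and polyneuropathy, summaries will be broken down by outcomes (unknown, recovered, not yet recovered, recovered with sequelae and death", and does not name infusion-site reactions there. SAP 7.3.1.2 adds "Time from onset of Hypersensitivity to resolution will be presented with descriptive statistics" and an outcome breakdown. SAP 7.3.1.3 does the same for polyneuropathy: "Summaries for total number of Polyneuropathy will be broken down by Outcomes". Protocol 11.1.4.1.3 and 11.1.4.1.4 agree.

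For the remaining local skin data, SAP 7.3.3 states that "assessment of nodules and hematomas (number and severity) will be listed but not summarized", along with the erythema, edema and Draize scores. Protocol 11.1.4.1.6 also has them as "will be listed but not summarized".

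On data collection, Protocol 10.1.3 has every infusion-site reaction reported as an AESI, including those the investigator judges not clinically significant. Protocol 10.1.1 records a resolution date and one of five outcomes for each AE. It also requires a change in severity to be entered as a separate event.

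**The concern.** SAP 1 explains that the primary analysis was moved from local skin scores to AESIs, on regulatory advice that singled out infusion-site skin reactions. Protocol 8.2 gives long-term local reactions as a special focus. The AESI at the centre of that change nevertheless has the shortest analysis section of the three.

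For a product infused daily through two sites, a reader will want to know how many reactions occurred, how bad they were, and whether they went away. The plan answers the first two. On the third, Protocol 8.2 describes local findings so far as generally transient, and Protocol 9.2.9 foresees skin problems still unresolved at the last follow-up visit. No table in either document would support the first statement or count the second.

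**Working it through.** There is no calculation to reproduce: the study has no formal sample size evaluation, and the question is which tables are planned. The check sets the sections side by side.

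**Step 1. The three AESI sections (SAP 7.3.1.1 to 7.3.1.3).**

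| Planned summary | Infusion-site reactions | Hypersensitivity | Polyneuropathy |
|---|---|---|---|
| Events, exposure-adjusted rate, patients | 1 | 1 | 1 |
| Kaplan-Meier time to onset | 0 | 1 | 1 |
| Time to resolution | 0 | 1 | 1 |
| Breakdown by outcome | 0 | 1 | 1 |
| **Total** | **1** | **4** | **4** |

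Summaries that use recovery, sequelae or time to resolution (rows 3 and 4): 0 + 0 = 0 for infusion-site reactions, and 1 + 1 = 2 for each of the others.

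**Step 2. Does another table fill the gap?**

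- *General TEAE tables (SAP 7.3.4).* There are ten bulleted summaries. They classify by term, relatedness, severity, seriousness, discontinuation, dose adjustment or interruption, and time of onset. None uses recovery, sequelae or duration. The only outcome category present is in the overall table ("and TEAEs leading to death"), pooled over all TEAEs. So of the five outcomes collected, 5 − 1 = 4 appear in no table that covers infusion-site reactions.
- *Kaplan-Meier plots for the most common terms (SAP 7.3.4).* These show first onset only.
- *VAS pain (SAP 7.3.2).* It is tabulated by visit and is a primary measure. Protocol 10.1.3 asks for the pain felt at that moment, so it shows whether local pain continues. It does not show whether a nodule or other lesion has healed.
- *Disposition (SAP 6.2).* Reasons for discontinuation are tabulated, and Protocol 8.3.4 makes infusion-site reaction a separate reason. This shows who stopped, not what became of the reaction.
- *Local scores, nodules and hematomas (SAP 7.3.3).* Listings only.

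**Step 3. Are the data there?** Yes. Every reaction is an AESI record (Protocol 10.1.3) with an outcome and, where applicable, a resolution date (Protocol 10.1.1). Subjects who stop treatment also have infusion-site assessments at 1 month (Protocol 9.2.4) and at 2 and 3 months (Protocol 9.2.5), 1 + 2 = 3 in all. The number of planned tables of resolution at those visits is 0.

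**Step 4. Does the existing bullet transfer unchanged?** Almost. One patient can have many reactions, and a single reaction that changes grade produces more than one record (Protocol 10.1.1). Event rows can count records. Patient rows need a rule that places each patient in one category, and the bullets in SAP 7.3.1.2 and 7.3.1.3 do not give one.

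**The case against.** The strongest reply is that this concerns table format, not evidence. The study is descriptive with no confirmatory testing (Protocol 11.1.4.3.2), SAP 7.3.4 lists all AEs, and SAP 3.5.2 allows unplanned analyses to be reported in appendices. Consequential reactions would surface as serious TEAEs, as discontinuations under their own reason, or through the dermatology examination required for certain serious cases (Protocol 10.1.1.1). VAS pain by visit gives some view of persistence. There is also a plausible reason for treating these reactions differently, though neither document states one. Hypersensitivity and polyneuropathy arise as discrete cases, whereas infusion-site reactions may arise daily at newly chosen sites, and subjects entering the extension keep infusing, so open reactions at the cut are to be expected.

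Much of this stands. It limits the weight of the point and is why the fix stays small. It does not remove the point. The same listings cover hypersensitivity and polyneuropathy, and the sponsor still planned outcome tables for both. A high reaction count also makes a listing harder to read than a table.

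Two stronger readings are tempting. A reader might infer that the primary safety results are biased. They are not: counts, rates and percentages are unaffected by the missing breakdown. A reader might also infer that healing was not followed, or that the information is lost. The documents show the opposite, since outcome and resolution date are collected and follow-up site assessments are scheduled.

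**Conclusion.** The point holds as a gap in what the primary safety tables can show. Its size is 0 planned summaries of resolution for infusion-site reactions, against 2 for each of the other AESIs, and 0 of ten general TEAE summaries that would substitute. It is worth correcting because it concerns the AESI named for focus and the correction uses data already collected.

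The conclusion rests on these two documents. The SAP covers only the 12-month main study (SAP 1.1). The separate extension SAP and the data monitoring committee charter are not available here and might contain such a table. Protocol 11.1.4.1.6 says only that extension safety data will be analyzed in a similar way.

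**What to change.** Add to SAP 7.3.1.1 and Protocol 11.1.4.1.2 the outcome bullet already used in SAP 7.3.1.2 and 7.3.1.3: infusion-site reactions by the five collected outcomes, as events, exposure-adjusted rates, patient counts and percentages, overall and by preferred term.

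State that each patient is counted once, overall and within each preferred term, by worst outcome, and fix the order. One reasonable order is death, recovered with sequelae, not yet recovered, unknown, recovered. The order is a judgment; what matters is that it is written down before lock. The Protocol does not say what outcome is entered on a record superseded by a grade change, so a footnote should say how such records were coded.

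The cost is one or two extra tables, with no new data, visits or patients. The downside is that reactions still open at the data cut in subjects who continue infusing will appear as not yet recovered. A footnote should say so.

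Optionally, report the number and percentage of subjects who stopped treatment and had an unresolved reaction at the 1-, 2- and 3-month follow-up visits. This covers only those who stop, a selected group. It would also be limited to follow-up data available at lock (Protocol 11.1.6), because the analysis starts once all subjects have completed Month 12 (SAP 1.1).

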7.3.1.2. Hypersensitivity Analyses

- Summaries for total Number of Hypersensitivity cases (by SOC and PT), will be presented as number of events, event rates adjusted to exposure and patient counts and percentages.
- Time to onset of Hypersensitivity will be presented by Kaplan Meier figures. In these analyses, the patients who did not experience Hypersensitivity will be right censored at the time of the last visit.
- Time from onset of Hypersensitivity to resolution will be presented with descriptive statistics. Unresolved cases will be right censored at the last visit.
- Summaries for total number of Hypersensitivity will be broken down by Outcomes (unknown, recovered, not yet recovered, recovered with sequelae and death) and will be presented as number of events, event rates adjusted to exposure and patient counts and percentages.

7.3.1.3. Polyneuropathy Analyses

- Summaries for total Number of Polyneuropathy cases (by SOC and PT), will be presented as number of events, event rates adjusted to exposure and patient counts and percentages.
- Time to onset of Polyneuropathy will be presented by Kaplan Meier figures. In these analyses, the patients who did not experience Polyneuropathy will be right censored at the time of the last visit.
- Time from onset of Polyneuropathy to resolution will be presented with descriptive statistics. Unresolved cases will be right censored at the last visit
- Summaries for total number of Polyneuropathy will be broken down by Outcomes (unknown, recovered, not yet recovered, recovered with sequelae and death) and will be presented as number of events, event rates adjusted to exposure and patient counts and percentages.

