- Unrelated: Adverse event judged by the investigator as NOT having a reasonable suspected causal relationship to the investigational medicinal product

Action Taken

The investigator will describe the action taken in the appropriate section of the eCRF, as follows:

Action Taken:

- None
- Study Drug Stopped
- Study Drug temporarily interrupted
- Concomitant medication
- Other

Action Taken with Study Treatment:

- Dose Increased
- Dose Not Changed
- Dose Reduced
- Drug Interrupted
- Drug Withdrawn
- Not Applicable
- Unknown

Recording and Follow-up of Adverse Events

Adverse events will be recorded from informed consent to the final safety follow-up visit or the Early termination visit (if applicable). Subjects should be followed up for 3 months after receiving the last dose of study drug, and any AEs that occur during this time should be reported according to the procedures outlined above.

The subject will be followed as part of this protocol for 3 months after the last dosing.

All investigators should follow up subjects with AEs until the event is resolved or until, in the opinion of the investigator, the event is stabilized or determined to be chronic.

Documentation and Reporting of Adverse Events

AEs should be reported and documented in accordance with the procedures outlined below. All AEs occurring during the study must be documented on the relevant eCRF pages. The following data should be documented for each AE:

- Description of the symptom event
- Classification of "serious" or "not serious"
- Severity
- Date of first occurrence and date of resolution (if applicable)
- Action taken
- Causal relationship
- Outcome of event (unknown, recovered, not yet recovered, recovered with sequelae, death [with date and cause reported])

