1. PREFACE

This Statistical Analysis Plan (SAP) describes the planned analysis and reporting for NeuroDerm clinical trial ND0612H-012 (A multicenter, international, open-label, safety study of ND0612, a solution of levodopa/carbidopa delivered via a pump system as a continuous subcutaneous infusion in subjects with advanced Parkinson's Disease (BeyoND)), and was written in accordance with SOP 002 - Statistical Analysis Plan (NStat – [REDACTED] Procedure). The structure and content of this SAP provides sufficient details to meet the requirements identified by the FDA and International Conference on Harmonization of Technical Requirements for Registration of Pharmaceuticals for Human Use (ICH): E9 Guidance on Statistical Principles in Clinical Trials. All work planned and reported for this SAP will follow internationally accepted guidelines, published by the American Statistical Association, and the Royal Statistical Society, for statistical practice.

The following documents were reviewed in preparation of this SAP:

- Clinical Study Protocol ND0612H-012 Version 9.0 (global Amendment 8): issued on, July 11th 2019
- Case report form (CRF) for ND0612H-012
- ICH E9 Guidance on Statistical Principles for Clinical Trials.
- ICH E3 Structure and Content of Clinical Study Reports (CSRs)

This SAP describes the statistical analyses as it is foreseen before final database lock. The SAP will serve as a complement to the study protocol and supersedes it in case of differences between the SAP and the statistical sections of the protocol. In case of major differences, e.g. changes in the analysis related to the primary endpoint, a protocol amendment will be considered. The SAP may be updated during the study conduct and will be finalized before final database lock.

Based on FDA correspondences dated 27th of March 2019, Neuroderm was advised to focus its safety analysis on AE of Special Interest (AESI), specifically for Infusion Site Skin Reactions (ISR's). In addition, all cases of hypersensitivity reactions (e.g., diffuse skin rash, anaphylaxis and angioedema) should be considered AESI. Cases of Polyneuropathy were also considered as AESI.

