1.1. Scope

Study ND0612H-012 consists of two parts:

- The main study: all subjects will participate in the 12-month main study. The data from the main study will be included in the final study report and will constitute the primary analysis of the study. This Statistical Analysis Plan (SAP) covers the main study only. The primary analysis based on the data from the main study will be conducted once all subjects have completed the final treatment visit (Month 12 visit) of the main study.
- The optional treatment extension period: Subjects are allowed to continue to an extension period. This SAP does not cover this extension period. A separate SAP will define the analyses of the data from the optional treatment extension period.

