5. GENERAL ASPECTS FOR DATA ANALYSIS

5.1. General Methods

All data from all patients entered into the study will be included in patient data listings. The listings will be sorted by center, and patient number (and by visit, if applicable).

The data will be summarized using either descriptive statistics (number of non-missing observations, mean, median, SD, standard error of the mean (SEM), minimum and maximum) for continuous data or frequency counts and percentages for categorical data. For visit-specific data, the number of subjects with non-missing observations at the visit in question will be used as the denominator for percent calculations. Unknown, Not Done, Not Applicable and other classifications of missing data will not be considered.

The summaries will be broken down by treatment regimen (Regimen 1, Regimen 3) and by visit, as applicable. For demographic and other baseline characteristics and selected safety data, an overall column will be displayed in addition to the data broken down by the treatment regimen. Unscheduled or repeated assessments will not be included in summary tables but will be included in listings.

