7.4. Tolerability and Treatment Compliance

7.4.1. Tolerability

Tolerability will be assessed based on percentage of subjects that complete the 12-month treatment period of the study and the percentage of subjects who discontinue from the 12-month treatment period due to a TEAE. Time (days) from enrolment to discontinuation will be illustrated as Kaplan-Meier curves by treatment regimen. Patients who complete the study will be right censored at the date of last dose of study treatment during the 12-month study period. Time to discontinuation will also be explored by recruitment wave 1 and 2 following corrective actions for patients' retention.

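### The SAP right-censors unresolved hypersensitivity and polyneuropathy cases, but the only summary it names for time to resolution takes no account of censoring

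*SAP*

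**What the plan says.** Two of the three adverse events of special interest have a time-to-resolution summary under the SAP's primary analyses.

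- SAP 7.3.1.2: "Time from onset of Hypersensitivity to resolution will be presented with descriptive statistics. Unresolved cases will be right censored at the last visit".
- SAP 7.3.1.3: "Time from onset of Polyneuropathy to resolution will be presented with descriptive statistics. Unresolved cases will be right censored at the last visit".
- SAP 5.1 defines the summary for continuous data as "descriptive statistics (number of non-missing observations, mean, median, SD, standard error of the mean (SEM), minimum and maximum".
- SAP 5.4 rules out imputation for safety data and asks for observed-case summaries.
- Protocol 11.1.4.1.3 matches the SAP for hypersensitivity. Protocol 11.1.4.1.4 names descriptive statistics for polyneuropathy but has no censoring sentence.

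For other censored times the SAP names its method. In 7.3.4, "The time to first onset of each TEAE within each treatment group will be summarized with Kaplan-Meier methods". In 7.4.1, "Time (days) from enrolment to discontinuation will be illustrated as Kaplan-Meier curves by treatment regimen". Time to onset of the same two events is to be shown as Kaplan-Meier figures.

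**The concern.** A right-censored time says only that the event lasted at least that long. A plain mean or median has no place for that information, so an analyst must do something the SAP does not state: drop the unresolved cases, enter their censored times as if they were complete durations, or move to a survival method. Two analysts could report different durations from the same data. How long polyneuropathy or hypersensitivity persists is part of what a long-term safety study should describe, and cases still open at the last visit tend to be the long ones.

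**Working it through.** **Step 1: the text.** Time variables with a stated censoring rule in the SAP:

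| Time variable | Summary named | Censored at |
|---|---|---|
| Onset of hypersensitivity, polyneuropathy (7.3.1.2, 7.3.1.3) | Kaplan-Meier figures | last visit |
| First onset of common TEAEs (7.3.4) | Kaplan-Meier | last visit |
| Discontinuation (7.4.1) | Kaplan-Meier curves | last dose in the 12 months, for completers |
| Resolution of hypersensitivity, polyneuropathy (7.3.1.2, 7.3.1.3) | descriptive statistics | last visit |

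Only the last row lacks a censoring-aware method.

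**Step 2: direction of error.**

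- *Censored times counted as complete.* Each recorded time is at most the true one, so the mean is too low whenever any case is unresolved. The median is too low only if cases are censored before the true median.
- *Resolved cases only.* If duration is unrelated to when the event starts, short events are over-represented and the summary is too low. The direction can reverse. Suppose half the cases start early, last 4 months and resolve, and half start late, last 1.5 months and are all still open at the last visit. The true mean is (4 + 1.5)/2 = 2.75 months; the resolved-only mean is 4.

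**Step 3: illustration of size.** The documents state no figure to reproduce. Assumed inputs, none of them from the documents: onset uniform over Months 0–12, no dropout, follow-up to Month 12, exponential duration with median 6 months.

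- λ = ln 2/6 = 0.1155 per month; 12λ = 1.386; true mean 1/λ = 8.66 months.
- Unresolved share = (1 − e^(−12λ))/(12λ) = (1 − 0.25)/1.386 = 0.541.
- Mean, censored counted as complete = (1 − 0.541)/0.1155 = 3.97 months, or 46% of the true mean.
- Median, censored counted as complete: solve e^(−λt)(1 − t/12) = 0.5. At t = 3.26, 0.686 × 0.728 = 0.50.
- Median, resolved only: solve (1 − e^(−λt)) − [1 − (1 + λt)e^(−λt)]/(12λ) = 0.459/2 = 0.229. At t = 2.55, 0.255 − 0.026 = 0.229.
- Large-sample Kaplan-Meier on the same inputs returns about 6 months (5.97–6.05 in simulation).

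Other durations, solved the same way. For a Month 15 end, the factor (1 − t/12) becomes 1 up to t = 3 and (15 − t)/12 after that. Cells are Month 12 / Month 15:

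| True median (months) | Unresolved | Median, censored as complete | Median, resolved only |
|---|---|---|---|
| 0.5 | 6% / 0.1% | 0.47 / 0.50 | 0.47 / 0.50 |
| 1 | 12% / 1.5% | 0.89 / 1.00 | 0.87 / 0.98 |
| 3 | 34% / 17% | 2.15 / 3.00 | 1.91 / 2.32 |
| 6 | 54% / 38% | 3.26 / 4.69 | 2.55 / 3.20 |
| 12 | 72% / 61% | 4.31 / 6.34 | 2.99 / 3.82 |

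With lognormal durations (true median 6, Month 12 end), simulated medians are 3.5 and 3.2 for log-SD 1, and 4.2 and 4.8 for log-SD 0.5 (as complete, then resolved only). The size depends on the assumed shape.

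**Step 4: the censoring visit.** Month 12 against Month 15 moves the third row from the naive 2.15 to 3.00 and the fourth from 3.26 to 4.69, so the undefined 'last visit' matters if a plain summary is used. The SAP states "This Statistical Analysis Plan (SAP) covers the main study only", yet protocol 10.1.1 says "Subjects should be followed up for 3 months after receiving the last dose of study drug", protocol 11.1.6 brings in safety follow-up data available at lock, and extension entrants have later visits still.

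**The case against.** The strongest reply is that nothing here contradicts itself. SAP 5.1 lists names of statistics, not estimators, and a median can be a Kaplan-Meier median. Right censoring is survival-analysis language, and the specific bullet may be read as qualifying the general section. The protocol synopsis already pairs Kaplan-Meier figures with descriptive statistics for time to onset of these events. SAP 5.4's bar on imputation also weighs against entering a censoring date as a resolution date. The next bullet in each section tabulates outcomes, including cases not yet recovered, and all AEs are listed. Protocol 10.1.1 has investigators follow AEs until they are resolved, stable or chronic.

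Much of this stands. A reader might infer that the sponsor intends a biased analysis; the text does not show that, since a careful analyst could choose Kaplan-Meier. But the benign reading is not written down. A mean, SD, SEM and maximum have no obvious censored version in SAP 5.1, and the observed-case rule in SAP 5.4 could equally lead to a resolved-only summary. The outcome table shows how many cases are open; it does not correct a reported duration.

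**Conclusion.** The point holds as an unspecified estimator: the stated censoring rule and the stated summary do not fit together without a choice that the SAP leaves to the analyst. It should be fixed, but it is one supporting descriptive item, and no test, power or sample size rests on it.

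Two stronger conclusions are tempting. One is that duration will always be understated. That is true of the mean when censored times are counted as complete; it is usual, but not certain, for a resolved-only summary. The other is to take the illustrated medians as a forecast for this trial. They rest wholly on assumed onset, duration and follow-up, because the documents give no event counts or durations. What can be said is that events lasting weeks are hardly affected, while events lasting many months could be reported at roughly half their true median or less. Longer follow-up of extension entrants, if used, would reduce the effect.

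**What to change.** In SAP 7.3.1.2 and 7.3.1.3, replace the sentence on time to resolution with text to this effect: time from onset to resolution will be summarised by the Kaplan-Meier method, giving the proportion unresolved at pre-specified times (for example 1, 3 and 6 months), the median with 95% CI or 'not reached', and the numbers resolved and censored. Name the visit used for censoring, including for subjects who enter the extension. Label any plain mean or median 'resolved cases only'.

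The cost is two bullets and a method already programmed for other endpoints. Protocol 11.1.4.1.3 and 11.1.4.1.4 can be aligned at the next amendment. Alternatively, the sponsor can rely on the SAP preface, under which the SAP "supersedes it in case of differences between the SAP and the statistical sections of the protocol". The same preface says an amendment will be considered for major differences such as changes to the primary-endpoint analysis, so the sponsor should record why this is or is not one. If the database is already locked, protocol 11.1 calls for the change to be documented in the study report.

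There are two downsides. With few cases the median is imprecise or not reached: in simulations of 10 cases under the exponential assumptions, with follow-up to Month 12 / Month 15, it was not reached in 22% / 8% of runs for a true median of 6 months and in 61% / about 46% for 12 months. The proportion unresolved at fixed times remains usable: at 3 months, with a true median of 6, it averaged 0.71 against a true e^(−3λ) = 0.71, with SD 0.14–0.16. Kaplan-Meier also assumes that censoring is unrelated to resolution, which is doubtful if subjects leave because of the event, so the report should say so.
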